#### **2 STATISTICAL HYPOTHESES**

For the primary endpoint (treatment retention at Injection 2), the null and alternative statistical hypotheses are:

 $H_0$ : retention rate of RI – SoC induction  $\leq$  -10% (NI margin of 10%)

 $H_A$ : retention rate of RI – SoC induction > -10%.

The criterion for success (ie, demonstrating NI) at an IA or final analysis is based on the posterior probability of retention rate difference (RI - SoC) > -10%. The NI of RI to the SoC induction will be declared if the posterior probability is higher than 96%. The 96% critical value is chosen so that the overall 1-sided Type I error is less than 10%.

#### 2.1 Multiplicity Adjustment for the 2 Interim and the Final Analyses

Two interim analyses will be performed at N $\geq$ 120 and N $\geq$ 240 randomised participants treated with TM BUP (respectively) to allow early declaration of NI of RI to SoC induction with respect to treatment retention at Injection 2 (see Section 5.8 for details). At each IA, the criterion of NI is the posterior probability of retention rate difference (RI – SoC) > -10% being 96% or greater.

A 96% critical value at each IA and the final analysis is chosen to provide overall 1-sided Type I error less than 10%. Table 3 shows 1-sided Type I error at each IA, final analysis and overall, for 5 null hypothesis scenarios for 10% NI margin where the retention rate of RI is truly 10% less than control.

Table 3. 1-Sided Type I Error at Each IA, Final Analysis and Overall, Under Different Null Scenarios for 10% Non-inferiority Margin

	Assumptions of Retention Rate at Injection 2				
Analysis	P soc =0.65	P soc =0.70	P soc =0.75	P soc =0.80	P soc =0.85
Analysis	P R =0.55	P R =0.60	P R =0.65	P R =0.70	P R =0.75
IA at n=120	0.0426	0.0439	0.0446	0.0462	0.0467
IA at n=240	0.0258	0.0267	0.0258	0.0263	0.0276
FA at n=489	0.0232	0.0234	0.0237	0.0235	0.0235
Overall	0.0916	0.0941	0.0941	0.0959	0.0978

FA=Final Analysis; IA=Interim Analysis;  $P_R$ =retention rate of RI;  $P_{SoC}$ =retention rate of SoC induction; SoC=standard of care

Note: A total of 100,000 simulations were performed per scenario.

If NI is declared at the first IA, then the second IA might not be performed. The final analysis will be performed irrespective of the number of IAs.

#### 3 SAMPLE SIZE AND POWER FOR SUB-STUDY

The sample size for the sub-study is based on the required sample size for the main study and the assumed premature discontinuation rate in the sub-study, as the sub-study is an integral

part of the main study. Approximately 489 participants will be randomised in a 2:1 ratio to RI or SoC induction arms. Under the assumption of 70% retention rate at Injection 2 for both arms and with 2 planned IAs at 120 and 240 participants, a total of 489 participants will provide 77.2% power to conclude NI of RI to SoC induction under 10% NI margin. Table 4 provides cumulative power at the 2 planned IAs and the final analysis under different assumptions of retention rate at Injection 2, with scenarios of same retention for both arms or greater retention rate for RI. The assumption about the possible retention rate at Injection 2 was based on the retention rates observed in the 2 previous Phase 3 studies (RB-US-13-0001 and RB-US-13-0003). In these 2 previous Phase 3 studies, among the participants with OUD who initiated SoC induction, about 65.7% (or 72.1%) received their second RBP-6000 injection. For injection route users, the retention rate was about 64.4% (or 70.1%).

Table 4. Cumulative Power at 2 Planned Interim Analyses and Final Analysis Under Different Assumptions of Retention Rate at Injection 2

		Assumptions	of Retention Rate	at Injection 2	
Analysis	$P_{SOC}=P_{R}=0.65$	$P_{SoC}=P_{R}=0.70$	$P_{SoC}=P_{R}=0.75$	$P_{SoC}=P_{R}=0.80$	P SoC =P R =0.85
IA at n=120	0.277	0.294	0.324	0.369	0.449
IA at n=240	0.489	0.517	0.564	0.627	0.723
FA at n=489	0.742	0.772	0.817	0.869	0.932
	P soc =0.65	P SoC =0.7	P soc =0.75	P SoC =0.80	P SoC =0.85
	P R =0.70	P R =0.75	P R =0.80	P R =0.85	P R =0.90
IA at n=120	0.498	0.538	0.598	0.679	0.804
IA at n=240	0.780	0.816	0.867	0.922	0.974
FA at n=489	0.963	0.976	0.988	0.996	>0.999
	P soc =0.65	P SoC =0.70	P soc =0.75	P SoC =0.80	P SoC =0.85
	P R =0.75	P R =0.80	P R =0.85	P R =0.90	P R =0.95
IA at n=120	0.726	0.781	0.844	0.924	0.988
IA at n=240	0.945	0.968	0.986	0.998	>0.999
FA at n=489	0.998	0.999	>0.999	>0.999	>0.999

FA=Final Analysis; IA=Interim Analysis; PR=retention rate of RI; PSoC=retention rate of SoC Induction; SoC=standard of care

Note: A total of 100,000 simulations were performed per scenario.

#### 4 POPULATIONS FOR ANALYSIS

This section describes the analysis populations for the final analysis. For details on the analysis population for the IA, see Section 5.8.

**Table 5. Populations for Analysis** 

Population	Description
Screened	All participants who sign the informed consent form.
Sub-study Randomised Population (SRP)	The SRP will comprise all participants who give informed consent and are randomised to sub-study treatment. The participants will be analysed corresponding to the induction arm to which they were randomised (ie, planned arm).
Sub-study Full Analysis Set (SFAS)	The SFAS will comprise all participants who are randomised to sub-study treatment and receive the first dose of TM BUP and do not demonstrate idiosyncratic response to the first dose of TM BUP (ie, allergic / hypersensitivity reaction to TM BUP as recorded on the electronic case report form [eCRF] disposition). The participants will be analysed corresponding to the induction arm they received ("as treated", ie, actual arm), given that logistically it is highly unlikely for them to receive the induction arm that they were not randomised to since the randomised arm triggers eCRF forms corresponding to the schedule of events for that arm. Participants who were randomised and inducted with neither RI or SoC (which is a key protocol deviation) will be excluded from the SFAS. The SFAS will serve as the primary population for the analysis in this sub-study.
Evaluable Population for Treatment Retention/Discontinuation a	For analysis pertaining to treatment retention and time-to-treatment discontinuation, the SFAS participants who discontinue treatment within the sub-study due to not meeting Inclusion/Exclusion criteria will be also excluded. The participants will be analysed corresponding to the induction arm they received ("as treated", ie, actual arm).

a Note that this population is described in the protocol but was not given a distinct population name. It is named in this statistical analysis plan for ease of reference and clarity in estimand and analysis specifications.

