3. SUB-STUDY ENDPOINTS

The primary endpoint of this sub-study is treatment retention at Injection 2 defined as the proportion of participants receiving Injection 2 at the Week 2 visit among those who received at least 1 dose of TM buprenorphine for induction and did not demonstrate idiosyncratic response to the first dose of TM buprenorphine. Participants who discontinue treatment due to not meeting Inclusion/Exclusion criteria will be excluded.

The secondary endpoints of this sub-study are the following:

- time to treatment discontinuation from the first dose of TM buprenorphine used for induction during the Open-label Treatment Period (OLTP) defined as the number of days from the first dose of TM buprenorphine until the last scheduled visit observed during the OLTP. Participants receiving the third RBP-6000 injection (i.e., the first randomised injection) will be censored administratively at the end of the OLTP; otherwise participants will be viewed as having discontinued treatment at their last scheduled visit observed during the OLTP. Participants discontinued due to idiosyncratic response to the first dose of TM buprenorphine or not met meeting Inclusion/Exclusion criteria will not be included.
- adverse events up to Injection 2, and between Injections 2 and 3

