8.1.3. Groups for Comparison

Data will be summarised and comparisons will be made (where applicable) by RBP-6000 induction arm: rapid induction and SoC induction.

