8.4.2. Sub-study Full Analysis Set

The Sub-study Full Analysis Set (SFAS) will serve as the primary population for the analysis in this sub-study. The SFAS will comprise all participants who are randomised to sub-study treatment and receive the first dose of TM buprenorphine and do not demonstrate idiosyncratic response to the first dose of TM buprenorphine. The participants will be analysed corresponding to the induction arm they received. For analysis pertaining to treatment retention and time-to-treatment discontinuation, the participants who discontinue treatment due to not meeting Inclusion/Exclusion criteria will be excluded. The analysis population for the IA is defined in Section 8.10.

8.5. Primary Endpoint Analysis: Treatment Retention at Injection 2 (received at Week 2 visit)

Retention rate will be estimated by Bayesian beta-binomial model using non-informative uniform prior, i.e., Beta (1,1), within individual induction arms. The posterior distribution of retention rate difference between the 2 arms will be obtained and utilised to calculate the posterior probability of non-inferiority of the rapid induction to SoC induction using a 10% NI margin or a favourable trend of the rapid induction over the SoC induction. The criterion for success (i.e., demonstrating NI) is based on the posterior probability of retention rate difference (rapid – SoC) greater than -10%. The NI of rapid induction will be declared if the posterior probability is at 96% or greater. If the NI is declared, the posterior possibility for superiority of rapid induction over SoC induction will be evaluated.

8.6. Secondary Endpoint Analysis: Time to Treatment Discontinuation from the First Dose of TM Buprenorphine Induction

The time from the first dose of TM buprenorphine to treatment discontinuation will be presented by induction arm using a Kaplan-Meier (KM) curve within the randomisation strata (UDS fentanyl negative vs. positive at the day of first dose of TM buprenorphine) and for overall. Participants receiving the third RBP-6000 injection (i.e., the first

randomised injection) will be censored administratively at the end of the OLTP. Retention rate (with 95% CI) at specific time point will be estimated using KM product limit method for each induction arm. Hazard ratio (with 95% CI) of RBP-6000 rapid induction to SoC induction will be estimated using a Cox proportional hazard model, with arm as a single covariate, stratified by the randomisation strata.

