## **Development of Statistical Analysis Plan Template**

Table 2. Primary and Secondary Estimands

	Estimand Attributes			
Statistical	Variable/			PLS
Category	Endpoint	Population a	IES	(Analysis)
Primary Obj	ective: To compare treatment retention of partici	pants following rapid induction	or SoC induction of	onto RBP-6000 with respect to:
Primary Efficacy Endpoint	Treatment retention at Injection 2, defined as the proportion of participants receiving Injection 2 at the Week 2 Visit among those who received at least 1 dose of TM BUP for induction and did not demonstrate idiosyncratic response to the first dose of TM BUP. Participants who discontinue treatment within the sub-study due to not meeting Inclusion/Exclusion criteria will be excluded.	Evaluable Population for treatment retention/discontinuation	Not applicable: Intercurrent events are not relevant for this endpoint.	Retention rate will be estimated by Bayesian beta-binomial model using non-informative uniform prior, ie, Beta (1,1), within individual induction arms. The posterior distribution of retention rate difference between the 2 arms will be obtained and utilised to calculate the posterior probability of non-inferiority of the RI to SoC induction using a 10% non-inferiority margin or a favourable trend of the RI over the SoC induction. The participants will be analysed corresponding to the induction regimen used ("as treated" b ).
Primary Efficacy Endpoint/ Sensitivity Analysis	As primary	As primary	As primary	As primary. The participants will be analysed corresponding to the induction arm to which they were randomised ("as randomised" ').
Secondary Endpoint 1	Time to treatment discontinuation from the first dose of TM BUP used for induction during the OLIS, defined as the number of days from the first dose of TM BUP from the most recent induction attempt until the last scheduled visit observed during the OLIS.	As primary	Not applicable: Intercurrent events are not relevant for this endpoint.	KM curve presented by the induction arm within the randomisation strata (UDS fentanyl negative vs. positive at the day of first dose of TM BUP) and overall. Participants receiving Injection 3 will be censored administratively at the end of the OLIS; otherwise, participants will be viewed as having discontinued treatment at their last scheduled visit observed during the

Table 2. Primary and Secondary Estimands

	Estimand Attributes				
Statistical	Variable/			PLS	

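### Two SAP rules in the sub-study primary analysis go beyond the protocol, and the planned sensitivity analysis cannot show their effect

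*SAP*

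**What the plan says.** **Protocol, Appendix 22.9.** Section 8.4.2: "The SFAS will comprise all participants who are randomised to sub-study treatment and receive the first dose of TM buprenorphine", without an idiosyncratic response to that dose. Retention analyses also drop participants who discontinue for unmet entry criteria. There is no other exclusion. The same section adds: "The participants will be analysed corresponding to the induction arm they received". Section 8.1.3 allows for two groups: "comparisons will be made (where applicable) by RBP-6000 induction arm: rapid induction and SoC induction". Section 3 defines retention as the "proportion of participants receiving Injection 2 at the Week 2 visit".

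**SAP, population.** Table 5 adds an exclusion: "Participants who were randomised and inducted with neither RI or SoC (which is a key protocol deviation) will be excluded from the SFAS". The Evaluable Population is drawn from the SFAS and inherits it, and section 5.8 applies that population at the interims. Footnote a says of the Evaluable Population: "Note that this population is described in the protocol but was not given a distinct population name".

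**SAP, endpoint.** Table 2 repeats the protocol definition: "Treatment retention at Injection 2, defined as the proportion of participants receiving Injection 2 at the Week 2 Visit among those who received" at least one TM buprenorphine dose. The sentence above Table 6 in 5.3.1 agrees. Row 2 of Table 6, and of Table 7 for the interims, nevertheless assigns Yes to someone who missed Injection 2 but received Injection 3.

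**SAP, sensitivity.** Section 5.3.3 repeats the analysis by planned arm, and Table 2 gives its endpoint and population as those of the primary. Table 5 justifies the as-treated grouping "given that logistically it is highly unlikely for them to receive the induction arm that they were not randomised to".

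**SAP, declared changes.** Section 1 says the protocol's plans are left unmodified. The visible bullets of 6.2 list neither rule, though a line there may be redacted.

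**The concern.** Both rules act on events after randomisation, in a trial where site and participant know the induction arm. Removing participants can change an arm's observed retention rate. Recoding a miss as a success raises it. If either happens more in one arm, the estimated difference moves relative to the quantity the protocol defines. The stated type I error is indexed only by retention rates, so it makes no allowance for this.

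Some handling of people inducted by neither method was needed, because an as-treated comparison of two arms has no place for them. But the SAP does not define the category. SAP 5.6.1 keeps a display category of under 7 days for SoC participants who were injected, which suggests, without settling it, that short SoC inductions stay in.

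Row 2 of Table 6 is also reasonable as a measure of retention, since Protocol 6.6 counts completing Injection 3 as completing the sub-study. It is still not the stated endpoint. Protocol 9.4.2 describes Week 6 randomisation as following two 300-mg doses, while row 2 provides for someone who reaches Injection 3 without Injection 2. These passages need to be reconciled.

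The sensitivity analysis is where a reader would look for the effect of such choices. It keeps the population and the scoring and relabels arms in which crossover is expected to be rare, so it will nearly duplicate the primary result.

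**Working it through.** **Inputs.** Looks at 120, 240 and 489 participants, 2:1 (SAP 2.1 and 3), taken as 80/40, 160/80 and 326/163. Beta(1,1) prior in each arm, margin 10 points, success at posterior probability 0.96 or more (SAP 2.1, 5.3.2). Null scenarios from SAP Table 3.

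**Formula.** With x retained of n in each arm, P = ∫ f_S(t)·[1 − F_R(t − 0.10)] dt. Here f_S is the Beta(1 + x_S, 1 + n_S − x_S) density for SoC and F_R is the Beta(1 + x_R, 1 + n_R − x_R) distribution function for rapid. Error and power follow by summing binomial probabilities exactly over the three looks.

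**The plan's own figures, with no exclusion or recoding.** Overall type I error for SoC 65%, 70%, 75%, 80%, 85% with rapid 10 points lower: 9.29%, 9.33%, 9.41%, 9.50%, 9.75% (stated 9.16%, 9.41%, 9.41%, 9.59%, 9.78%). Power at 70%/70%: 77.4% (stated 77.2%). The stated design reproduces, with less than one point of room below 10%.

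**Shares below are assumed; the documents give none.** Error is measured against the protocol endpoint in all dosed participants, at SoC 70% and rapid 60%.

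*Recoding (exact).* Recoding a share d of an arm adds d to its scored rate.

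| Recoded | Type I error |
|---|---|
| none | 9.3% |
| rapid only, 1 of 326 (0.3%) | 10.3% |
| rapid only, 0.5% | 10.9% |
| rapid only, 1% | 12.7% |
| both arms, 1% | 9.35% |
| SoC only, 1% | 6.8% (power at 70%/70% falls to 70.7%) |

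*Exclusion (simulation, 400,000 runs, Monte Carlo error about 0.1 point).* Excluding a share e, all failures, moves the analysed rapid rate from 0.60 to 0.60/(1 − e): 0.606, 0.612 and 0.619 for e = 1%, 2% and 3%. Excluding e, all retained, moves it to (0.60 − e)/(1 − e), which is 0.592 at 2%.

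| Excluded | 1% | 2% | 3% |
|---|---|---|---|
| rapid only, all failures | 11.2% | 13.6% | 16.3% |
| rapid only, at the arm's own rate | 9.4% | 9.3% | 9.2% |
| rapid only, all retained | 8.1% | 7.2% | 6.2% |
| both arms, all failures | 9.0% | 8.8% | not run |

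Excluding 2% of SoC only, all failures, gives an error of 5.9%, and power at 70%/70% falls from 77% to 67%. Excluding 2% of SoC only, all retained, gives 11.2%.

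*Other four null scenarios, rapid arm only.* Excluding 1% failures gives 10.9% to 13.2%; 2% at the arm's own rate, 9.2% to 10.0%; 2% all retained, 7.0% to 8.0%. Recoding 1% gives 12.5% to 14.2%.

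**How few participants can decide a result.** At the final look with SoC 114/163, rapid needs 220/326 (P = 0.961), and 219/326 gives 0.9545. One excluded failure added back (220/327) gives 0.957. So at the boundary one participant under either rule reverses the conclusion. At 228/326, about 70% in both arms, P is 0.991 and it takes 9 rescored or 13 added back.

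**The case against.** The plan is not silent on these participants. SAP 5.7.6 repeats the primary endpoint analyses in the group inducted by neither method. SAP 5.2.2 and 5.6.1 tabulate who received each injection. A beta-binomial posterior depends only on counts, so a careful reader could reassemble much of the missing result. Both rules are also written openly in the SAP before the final analysis, and the protocol expects the SAP to add detail.

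The error exceeds 10% only if a rule acts mainly in one arm. Balanced or outcome-neutral use gives 8.8% to 9.4% in the main scenario. Few people may be affected: Table 5 treats such inductions as a key deviation, and if Injection 3 generally follows two doses, row 2 may be nearly empty. Measured against the endpoint as Table 6 scores it, recoding inflates nothing. And one repeat that changes arm, population and scoring together cannot separate the two rules.

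Most of this limits the size of the problem, and that part stands: size and direction are unknown. It does not close the gap. No planned output gives the posterior probability under the protocol's definition with these participants included, and 5.7.6 does not say by which arm it groups people who have no actual arm. The protocol (Appendix 22.9, 8.1.1) says deviations from its analyses will be outlined in the SAP, so being visible in Tables 5 to 7 is not the same as being declared. The bundling objection is fair and is met by reporting numbers excluded and recoded by arm. The point about footnote a is minor, because the exclusion sits in the SFAS row and is only inherited.

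**Conclusion.** The concern holds. Two post-randomisation rules shape the sub-study's primary analysis without being in the protocol or the visible change list. Row 2 of Table 6 also departs from the SAP's own definition of the endpoint. The one planned sensitivity analysis cannot show the effect of either rule.

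What this does to the result cannot be known from the documents. Under assumed shares of 0.3% to 3% of an arm, at SoC 70% and rapid 60%, the type I error ranges from about 6% to 16% against a stated 9.41%. It stays near 9% when the rules act equally in both arms or regardless of outcome. With so little room below 10%, even one rapid-only recoding matters at the margin, whereas a comfortable result would survive several.

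This is a worthwhile, inexpensive improvement and not a flaw in the design. The protocol's own exclusions, the primary model and the 96% threshold are not in question.

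**What to change.** 1. Add to SAP 5.3.3, at each interim performed and at the final analysis, one repeat of the primary beta-binomial model by planned arm. Keep the protocol's exclusions, include participants inducted by neither method, and count as retained only those who received Injection 2 at the Week 2 visit. Leave the primary analysis unchanged.
2. Define the neither category from dosing records, without reference to Injection 2 status. State where SoC inductions under 7 days fall. Report the numbers excluded and recoded by planned arm, so that the two rules can be told apart.
3. State that the 5.7.6 analysis of this group is by planned arm, on a set that contains them.
4. List both rules and the interim population in SAP 6.2, unless a redacted line already does. Align Table 2 and the 5.3.1 text with Table 6, correct Table 5 footnote a, and reconcile row 2 of Tables 6 and 7 with Protocol 9.4.2.

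Item 1 matters most; items 3 and 4 are wording. The cost is SAP text and one more run of an existing model, with no new data and no new simulation. The one drawback is that the added result may be slightly less favourable and would need explaining if it differs from the primary.
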